1.1 BiRd medication schedule (one cycle)

Lenalidomide will be given for days 1-21 followed by a 7 day rest period for each 28-day cycle.

*Dexamethasone at a dose of 20mg on Days 1, 8, 15, 22 will be used for subjects ≤ 75 years old.

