Due to the potential increased risk of developing secondary primary malignancies associated with lenalidomide treatment, patients will be advised to undergo regular cancer screenings as part of standard of care. Monitoring for development of acute leukemia and Hodgkin's lymphoma will be performed by review of regular blood work, chemistry panel, and LDH at each visit including during follow-up. Particular attention will be paid to the complete blood count differential with a low threshold to investigate emerging cytopenias or altered differential with either bone marrow biopsy or PET scanning if clinically indicated. In addition, men and women will be advised to have a yearly skin exam by a dermatologist and regular colonoscopy screening (every 5 years or earlier, depending on GI recommendations). Women will also be advised to have yearly mammograms and regular cervical cancer screening. Men will also be advised to undergo yearly Prostate-Specific Antigen (PSA) testing.

For information on the risk of venous thromboembolism with combined oral contraception see **Appendix III: Risks of Fetal Exposure, Pregnancy Testing Guidelines and Acceptable Birth Control Methods.**

Cycles will be repeated every 28 days. Patient will return to clinic every 28 days for evaluation of toxicity and response and will remain on study until progression of disease, toxicities become excessive, or until discontinuation for another reason (see Section 9.2). Doses may be modified due to side effects.

Patients who achieve a resolution of monoclonal gammopathy as detected on serum immunofixation or achieve a plateau of disease (no change in quantitative M-spike or free light chains) for > 2 cycles will be transitioned to maintenance therapy. Maintenance therapy will consist of dexamethasone at a dose of 20mg weekly (given on days 1, 8, 15, and 22 of a 28 day cycle) and lenalidomide at a dose of 25 mg/day on days 1-21 of a 28 day cycle (a dose of 15mg/day days 1-21 of a 28 day cycle will be given to patients with a creatinine clearance of < 60 cc/min).

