
  ≥50% reduction in the level of the serum monoclonal paraprotein.  Reduction in 24h urinary light chain excretion either by ≥90% or to <200mg.  For patients with light chain only disease, then a 50% reduction in the difference between the involved and unininvolved free light chain level may be substituted for the M-protein measurement.  For patients with non-secretory myeloma only, ≥50% reduction in plasma cells in a bone marrow aspirate and on trephine bone biopsy, if biopsy is performed.  ≥50% reduction in the size of soft tissue plasmacytomas (by radiography or clinical examination).  No increase in size or number of lytic bone lesion (development of a compression fracture does not exclude response)
Stable Disease (SD) requires the following:

  Not meeting the criteria stringent complete response (sCR), complete response (CR), very good partial response (VGPR), or partial response (PR)
Plateau:

  Stable values (within 25% above or below value at the time response is addressed) 
Patients in which no significant change (<50% decrease or <25% increase from baseline) in the production rate of the monoclonal serum protein or Bence-Jones protein excretion and no new lytic lesions and/or plasmacytomas are detected.

Relapse from CR requires at least one of the following:

- Reappearance of serum or urinary paraprotein on immunofixation or routine electrophoresis, confirmed by at least one further investigation and excluding oligoclonal immune reconstitution.
- ≥5% plasma in a bone marrow aspirate or trephine bone biopsy.
- Development of new lytic lesions of soft tissue plasmacytomas or definite increase in the size of residual bone lesions (development of a compression fracture does not exclude continued response and may not indicate progression).
- Development of hypercalcemia (corrected serum calcium >11.5mg/dl or 2.8 mmol/l) not attributable to any other cause.

Progressive disease (PD) for patients not in CR requires one or more of the following:

- >25 increase in the level of the serum monoclonal paraprotein, which must also be an absolute increase of at least 5g/L and confirmed by at least one repeated investigation.

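### The immunofixation trigger for maintenance looks at serum only, so a patient with persisting urinary M-protein is stepped down early; the Appendix I plateau entry also holds a sentence that should go

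*Combined protocol and SAP*

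**What the plan says.** Section 9.1 makes the move to maintenance mandatory once either of two conditions is met.

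- Immunofixation trigger: "resolution of monoclonal gammopathy as detected on serum immunofixation". Urine is not mentioned.
- Plateau trigger: patients who "achieve a plateau of disease (no change in quantitative M-spike or free light chains) for > 2 cycles". Section 9.1 gives no tolerance or reference value, does not say which marker governs when several are measurable, and does not point to Appendix I.

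The regimen then changes: "Maintenance therapy will consist of dexamethasone at a dose of 20mg weekly", with lenalidomide. Clarithromycin is not listed. Section 4.1, by contrast, continues the randomized assignment until progression or unacceptable toxicity and mentions no such switch.

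The starting dexamethasone dose is 40 mg for everyone in sections 4.1 and 9.1, but the section 1.1 schedules carry a footnote: "Dexamethasone at a dose of 20mg on Days 1, 8, 15, 22 will be used for subjects ≤ 75 years old".

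The only numerical plateau wording is in Appendix I, which puts two sentences under one entry. The first is "Stable values (within 25% above or below value at the time response is addressed"; the second is "no significant change (<50% decrease or <25% increase from baseline". Partial response (PR) in the same table needs "≥50% reduction in the level of the serum monoclonal paraprotein" and, for urine, "Reduction in 24h urinary light chain excretion either by ≥90% or to <200mg". Complete response (CR) needs the original protein to be absent from both serum and urine by immunofixation.

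**The concern.** The immunofixation trigger tests one compartment in a disease that the protocol allows to be measured in two. Section 5.1 accepts patients on urinary M-protein alone or together with serum disease. In such a patient, serum immunofixation can turn negative while the urine still carries a measurable paraprotein. Followed as written, section 9.1 ends the induction regimen at that visit.

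What is at stake is the treatment actually delivered. As listed, maintenance removes clarithromycin, the only drug that differs between the arms, so on that reading an early switch shortens the experimental treatment. If section 4.1 governs and clarithromycin continues, what remains is an early dexamethasone reduction from 40 mg to 20 mg. A patient who started at 20 mg has no reduction.

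The plateau entry is a lesser problem. A site that looks up plateau to apply section 9.1 finds two limits with different reference points, and nothing says which one is meant.

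**Working it through.** No figure in the plan is in dispute, so the check sets the rules side by side and applies them to assumed patients.

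**Immunofixation trigger**

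Inputs: eligibility above 0.2 g/24 h urinary M-protein (5.1); PR urine limit of a fall of at least 90% or to below 200 mg (Appendix I); CR in serum and urine (Appendix I); 24-hour urine with immunofixation on Day 1 of each cycle (1.3 and 10.3).

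Assumed patient: baseline serum M-protein 1.0 g/dL and urine 1.0 g/24 h; now serum immunofixation negative and urine 0.5 g/24 h.

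- Change in urine: (0.5 − 1.0)/1.0 = −50%.
- PR by percentage: urine would have to be at most 1.0 × (1 − 0.90) = 0.1 g/24 h. Not met.
- PR by level: 0.5 g is 500 mg, against a limit of 200 mg. Not met.
- CR: not met, because urinary protein persists.
- Eligibility threshold: 0.5 exceeds 0.2 g/24 h, so the urine alone would still count as measurable disease.
- Section 9.1 trigger: met. The patient moves.

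If negative urine immunofixation is also required, the trigger is not met at this visit.

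**Plateau entry**

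Call the first Appendix I sentence the band: |current − reference| ≤ 25% of the reference. Call the second the baseline sentence: −50% < change from baseline < +25%, taking baseline as the pretreatment value. Serum PR is a change of −50% or lower, so PR and the baseline sentence cannot hold together for the same marker. Assumed examples, all with a baseline of 4.0 g/dL:

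| Course | Band | Baseline sentence |
|---|---|---|
| Steady at 1.6 (−60%, serum PR) | met | not met |
| 3.4 when response is addressed, now 2.2 | not met: (2.2 − 3.4)/3.4 = −35% | met: (2.2 − 4.0)/4.0 = −45% |
| 2.4 when response is addressed, now 3.2 | not met: (3.2 − 2.4)/2.4 = +33% | met: (3.2 − 4.0)/4.0 = −20% |
| Flat at 4.0 | met | met |

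The sentences disagree in both directions. The baseline sentence excludes a stable responder and admits patients whose marker is still moving.

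**Why the two parts belong together**

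Suppose only the immunofixation trigger is corrected. The assumed patient's serum value now stays at zero. If a site reads plateau on serum alone, more than two cycles of that stability move the patient even though the urine is still falling. If the band must hold for every marker measurable at baseline, urine also has to stay within 0.5 × 0.75 = 0.375 to 0.5 × 1.25 = 0.625 g/24 h around a reference of 0.5. If it does, the patient moves on a true plateau, which section 9.1 allows at any depth of response.

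**The case against.** Section 9.1 does not make maintenance depend on PR or CR. A patient whose urine fails PR has therefore not been moved in breach of the protocol, and a serum-only trigger could be a deliberate choice. This stands as far as it goes: the PR comparison shows how much disease can remain, not that a rule is broken. But the text gives no reason for leaving urine out, the protocol's own CR definition includes it, and the test is already done each cycle.

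The largest consequence, loss of clarithromycin, comes from the maintenance list in 9.1 being at odds with 4.1, which is a separate ambiguity. That also stands, and the effect is stated conditionally for this reason. Section 9.6 does treat BiRd therapy and maintenance as distinct phases, which supports reading the switch as a real change of regimen, but it does not settle the matter.

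On the plateau entry, the second sentence stands apart from the bulleted first one and reads like a description of stable disease. It may never have been meant to compete with the first. This is a fair reading, and it is the reason to delete the sentence from this entry.

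A reader might infer something stronger: that the two sentences put the same patient on the experimental regimen for a few cycles under one and until progression under the other. The documents do not support that.

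- Section 9.1 does not cite Appendix I. Its own words, no change, would not move a patient whose M-spike is still falling and would move one who is flat after a deep response.
- The contrast also needs a fixed reference for the band, which Appendix I does not state. Section 4.1.4 evaluates response every cycle. If the reference is the previous cycle's value, a marker falling 15% per cycle stays inside the band, and at cycle 3 it is 1 − 0.85³ = 38.6% below baseline, so both sentences are met.

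**Conclusion.** The concern holds in a limited form. Applied as written, the immunofixation trigger can step down a patient who still has measurable urinary M-protein. This rests only on the text of 9.1, 5.1 and Appendix I. The cost to that patient is an early dexamethasone reduction, for those who started at 40 mg, and early loss of clarithromycin if the 9.1 maintenance list is complete.

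The plateau point is secondary. The baseline sentence cannot be met by a patient holding a serum PR and does not belong in the entry. This assumes that baseline means the pretreatment value.

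A reader might also infer a biased primary comparison. The documents do not support that: patients are analysed as randomized (14.1), and randomization is blocked by site (14.3, Stratification Factors), so a site's reading of the rule applies to both arms. Power and sample size do not change. The worked patients are assumed, and the documents do not say how many real ones would follow these courses. The change is worth making because it is cheap and makes delivery of the regimen more consistent, not because the trial's validity depends on it.

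**What to change.** 1. In 9.1, require negative immunofixation in both serum and urine for the first trigger.
2. In Appendix I, delete the sentence measured from baseline from the plateau entry.
3. In 9.1, point the plateau trigger to the remaining 25% sentence, and require it for every marker measurable at baseline, serum and urine, so that one stable marker does not cause the switch while another is still changing.
4. Record the transition date and the criterion met, and report both by arm.

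The cost is two or three sentences in 9.1, one deletion in Appendix I and a case report form entry. No test is added, because serum and 24-hour urine studies with immunofixation are already scheduled on Day 1 of each cycle. The downside is that some patients move to maintenance slightly later and stay on the induction doses for that time.

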9.2 Early Termination of Study

Study-terminating events are listed below (to include?):

- *Early death (defined by death within 30 days of beginning therapy) deemed to be related to study treatment of more than 1 of the first 10 subjects.*
- *Early need for hospitalization (defined by hospitalization within 30 days of beginning therapy) of more than 5 of the first 10 subjects.*
- *If there is an unacceptable rate of Grade 4 toxicities (according to CTCAE version 4.0), as deemed by the research team, Celgene, or the Data Safety Monitoring Board.*

- *If >5% of patients develop a secondary primary malignancy on maintenance lenalidomide, the study will be halted and reviewed by the Investigator and Data Safety Monitoring Board before a decision will be made to proceed.*

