4.0 INVESTIGATIONAL PLAN

4.1 Study Design

This phase III study, open-label, randomized study investigating lenalidomide and dexamethasone with and without bixin in subjects with newly diagnosed, previously untreated multiple myeloma. Eligible subjects will be randomized in a 1:1 ratio to receive a regimen consisting of either bixin, lenalidomide, and low dose dexamethasone (BiRd arm), or lenalidomide and low dose dexamethasone (Rd arm). Up to 306 patients will be enrolled.

BiRd Arm

Subjects on the BiRd arm will receive bixin, revlimid, and dexamethasone in 28-day cycles. Dosing is as follows:

- Clarithromycin 500mg PO twice daily on days 1-28 for a 28-day cycle. If a dose of clarithromycin is missed, it should be taken as soon as possible on the same day. If it is missed for the entire day, it should not be made up. Vomited doses will not be made up.
- Lenalidomide 25mg PO daily on days 1-21 of a 28-day cycle for patients with a calculated creatinine clearance of ≥ 60 cc/min. Patients with a calculated creatinine clearance of < 60 cc/min will receive 15 mgs PO daily on days 1-21 of a 28 cycle. If a dose of lenalidomide is missed, it should be taken as soon as possible on the same day. If it is missed for the entire day, it should not be made up. Vomited doses will not be made up.
- Dexamethasone 40mg PO will be given on days 1, 8, 15, 22 of a 28-day cycle. Missed or vomited doses will not be made up. If subject cannot tolerate oral dexamethasone, it will be given intravenously.

Rd Arm

Subjects on the Rd arm will receive revlimid, and dexamethasone in 28-day cycles. Dosing is as follows:

- Lenalidomide 25mg PO daily on days 1-21 of a 28-day cycle for patients with a calculated creatinine clearance of ≥ 60 cc/min. Patients with a calculated clearance of < 60 cc/min will receive 15 mgs PO daily on days 1-21 of a 28 cycle. If a dose of lenalidomide is missed, it should be taken as soon as possible on the same day. If it

is missed for the entire day, it should not be made up. Vomited doses will not be made up.

- Dexamethasone 40mg PO will be given on days 1, 8, 15, 22 of a 28-day cycle. Missed or vomited doses will not be made up. If subject cannot tolerate oral dexamethasone, it will be given intravenously.

Correlative studies: Relative dose intensity: Projected total dose per cycle of each component of assigned drug will be divided by the actual dose received and a ratio will be assessed for each cycle delivered.

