9.0 Therapeutic Plan

9.1 Treatment

Patients who sign informed consent will be seen in clinic or in the hospital at New York Presbyterian Hospital-Weill Cornell Medical College, by their physician for pretreatment testing as outlined in section 6.0. All prescribers must be registered in the Celgene RevAssist® program in order to prescribe lenalidomide (Revlimid®). Subjects who complete pretreatment evaluations and meet all eligibility criteria may start treatment. All patients will be started on BiRd in 28-day cycles according to the following schedule:

For all subjects, **Dexamethasone** (Decadron®) will be given orally at a dose of 40 mg on days 1, 8, 15, and 22 for each subsequent cycle

For subjects on the BiRd arm only, **Clarithromycin** (Biaxin®) will be given orally at a dose of 500 mg twice a day, beginning on day 1 of cycle 1.

For all subjects, **Lenalidomide** (Revlimid®) will be given orally at a dose of 25 mg/day beginning on day 3 and ending on day 21 of cycle 1, and on days 1-21 of each subsequent cycle.

Due to the risk of thrombosis (see Section 8.5), all patients will begin thromboembolic prophylaxis with aspirin 81mg daily throughout treatment, starting on cycle 1 day 1. Aspirin-intolerant patients, or patients with a prior history of venous thrombosis, should receive prophylactic doses of daily low molecular weight heparin (LMWH). For patients who are unable to take aspirin or LMWH, other antithrombotic agents may be used at the investigators discretion. If warfarin is used, the INR should be monitored frequently to maintain within the goal range of 2-3. Concurrent use of recombinant erythropoietin to treat anemia is discouraged due to reports of increased thromboembolic events in patients receiving lenalidomide with erythropoietin. Concurrent use of erythropoietin requires full anticoagulation of patients with

therapeutic doses of LMWH or coumadin. Anticoagulation should be held for platelet counts <50,000/mm³.

Monitoring for Secondary Primary Malignancies

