13.0 DATA MANAGEMENT

13.1 Analyses and Reporting

This study will be conducted at The New York Presbyterian Hospital at the Weill Cornell Medical College. Clinical data will be collected under the supervision of one of the study investigators. Clinical data will be organized and recorded with the help of data managers located at the Cornell campus. Study design and data analysis will be implemented in collaboration with our biostatistician at Weill Cornell Medical College and data will be collected and tabulated on a monthly basis.

13.2 Data Safety Monitoring Board.

The Data Safety Monitoring Board (DSMB) at Weill-Cornell Medical Center will be composed of medical and statistical independent reviewers and will meet to review the efficacy and safety data and determine a risk/benefit analysis in this subject population. The purpose of the DSMB is to advise on serious safety considerations, lack of efficacy and any other considerations within the charge to the Committee. The DSMB may request additional meetings or safety reports as deemed necessary upon discussion with Celgene and its representatives. The PI, [name], will be the safety contact for all DSMB related analysis outcomes.

[name] office is located at: NYPH-WCMC
[name]
[name]

The phone number to [name] office is: [contact]

The DSMB may stop the study following review of results from each interim analysis. The first interim analysis will take place 3 months after the study begins subject accrual or after 10 patients have been enrolled, whichever occurs first, and will examine only safety information. A subsequent interim analysis will take place 6 months after the study begins subject accrual, and every six months thereafter, and will examine both safety and efficacy. The DSMB will also review the study after 66 PFS events have occurred across both arms for futility, (as outlined in the Statistical Considerations Section 14) including toxicity data, protocol adherence, and protocol deviations and enforce stopping rules if necessary. Efficacy and safety data summaries will be provided to the DSMB after each interim analysis.

“13.3 Study Monitoring and Auditing

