14.3 Stratification Factors

Patients will be stratified based on enrolling institution.

Blocked randomization will be performed at all participating sites. A series of randomized blocks will be generated for each participating site with a 1:1 allocation ratio. This will provide assurance that there will be an equal patient allocation to both treatment arms at any given participating site.

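### The first-10 stopping rules in Section 9.2 pool both arms, so they have little power for harm specific to BiRd and cannot attribute it; no scheduled DSMB look is tied to their completed 30-day data

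*Combined protocol and SAP*

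**What the plan says.** Section 9.2 (Early Termination of Study) lists events that would end the trial. Two are numeric and concern the first 10 subjects over 30 days from the start of therapy:

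- early death "deemed to be related to study treatment of more than 1 of the first 10 subjects";
- early "hospitalization within 30 days of beginning therapy) of more than 5 of the first 10 subjects".

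Neither names an arm. A third trigger, "If there is an unacceptable rate of Grade 4 toxicities", has no threshold and is left to the research team, Celgene or the DSMB. A fourth concerns second malignancies on maintenance. The list opens with "Study-terminating events are listed below (to include", followed by a question mark, so whether the rules are adopted is still open in the text.

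Section 4.1 says "Eligible subjects will be randomized in a 1:1 ratio". Section 14.3 (Stratification Factors) says "A series of randomized blocks will be generated for each participating site with a 1:1 allocation ratio" and gives no block size. Section 9.1 says "All patients will be started on BiRd in 28-day cycles according to the following schedule", then restricts clarithromycin to the BiRd arm.

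Section 13.2 places the first DSMB look, on safety only, at "3 months after the study begins subject accrual or after 10 patients have been enrolled, whichever occurs first". The next is at 6 months and then every 6 months. The DSMB may ask for additional meetings or reports.

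**The concern.** The safety question particular to this trial is whether adding clarithromycin to Rd is tolerable in patients aged 65 or over. The first-10 rules are the plan's only numeric early-toxicity limits, yet about half the subjects they count do not take clarithromycin. An excess on BiRd is averaged with Rd experience, and a breach would not show which arm caused it.

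The rules also need 30 days of follow-up per subject, while the first DSMB look is triggered by enrolment. If the Board relied on these limits, an unmet rule could reflect the pooling or open windows rather than an acceptable early safety profile, while accrual continued.

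**Working it through.** **Inputs.** Thresholds and the 30-day window: Section 9.2. Allocation: 1:1, Section 4.1. Accrual: about 9 per month (Section 14.2) or 10-15 per month (Section 4.2). Look times: Section 13.2. The plan states no operating characteristics for these rules, so there is no figure to reproduce. It also gives no expected 30-day death or hospitalisation rate, so every event rate below is an assumption.

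**Hospitalisation rule, no assumed rate needed.** More than 5 means at least 6. With 5 subjects on BiRd and no Rd hospitalisation, the largest possible count is 5. The trigger probability is 0 whatever the BiRd rate.

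**Hospitalisation rule, assumed rates, 5:5 split.** The count is Binomial(5, pB) + Binomial(5, pR), and the rule fires with probability Σ P(XB = k) · P(XR ≥ 6 − k). For pB = 0.8 and pR = 0.2:

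- k = 5: 0.3277 × 0.6723 = 0.2203
- k = 4: 0.4096 × 0.2627 = 0.1076
- k = 3: 0.2048 × 0.0579 = 0.0119
- k ≤ 2: 0.0003
- total: 0.340

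| BiRd rate | Pooled, Rd 10% | Pooled, Rd 20% | Same threshold, 10 BiRd subjects |
|---|---|---|---|
| 70% | 0.101 | 0.226 | 0.850 |
| 80% | 0.169 | 0.340 | 0.967 |

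The last column replaces the 5 Rd subjects with 5 more BiRd subjects, so it reflects a larger BiRd sample as well as the absence of pooling.

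The split matters. With 6 of the 10 on BiRd and no Rd events, the rule fires with probability 0.05, 0.26 and 1.0 at BiRd rates of 60%, 80% and 100%.

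**Death rule, at least 2 related deaths.** At a 20% BiRd rate and no Rd deaths, 5 BiRd subjects give 1 − 0.8⁵ − 5(0.2)(0.8⁴) = 1 − 0.3277 − 0.4096 = 0.263. Adding 5 Rd subjects at 1% gives 0.283. Ten BiRd subjects give 0.624. Pooling therefore costs this rule nothing in power; the limit is having only about 5 BiRd subjects.

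**Timing.** Assume even accrual, the first subject at time 0, therapy starting at enrolment and 30.4 days per month. The tenth subject enrols on day 9 × 30.4 / rate:

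| Accrual per month | Tenth enrolled (day) | First-10 windows closed |
|---|---|---|
| 9 | 30.4 | 1 |
| 10 | 27.4 | 0 |
| 15 | 18.2 | 0 |

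The tenth window closes at about month 1.6-2.0. By month 6 between 54 (9 × 6) and 90 (15 × 6) subjects would be enrolled. At 3 per month, 7 of 10 windows would be closed at the first look. Because the look is triggered no later than the tenth enrolment, all ten windows cannot have closed by then at any accrual rate. At planned rates the 10-patient limb comes first, so the 3-month limb is never used.

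**Counting by arm.** Ten BiRd subjects need about 20 enrolled. The twentieth window closes at 19/15 + 0.99 = 2.3 months (15 per month) to 19/9 + 0.99 = 3.1 months (9 per month).

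**False stops with 10 counted in each of two arms, equal true rates.** Related deaths at 5%: 0.086 for one set of 10, and 1 − (1 − 0.086)² = 0.16 for two. Hospitalisation at 30%: 0.047 becomes 0.09. Hospitalisation at 20%: 0.006 becomes 0.013.

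**The case against.** A reader might infer that the early check cannot detect harm confined to BiRd. The documents do not support that. Two related deaths on BiRd alone meet the death rule. The hospitalisation rule can fire once there are background Rd admissions or at least 6 BiRd subjects, and blocking within site with no stated block size does not guarantee 5:5 in the first 10 overall. The impossibility is confined to BiRd hospitalisations alone with 5 or fewer BiRd subjects.

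A reader might also infer that the early look disables the rules. Section 9.2 does not tie them to that look, and Section 13.2 does not mention them or fix a data cut-off on the day the tenth patient enrols. Deaths and hospitalisations are serious adverse events, reportable to Celgene within 1 business day (Sections 11.2 and 11.3.1), so counts can be known as windows close. The Grade 4 trigger is not limited to the first 10, the DSMB can call extra reviews, and the trial is open-label. No document describes a formal finding that the rule was not met, so false reassurance is a risk and not a stated step.

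Nor do the documents show that the rules were carried over from a single-arm study: Section 9.1 itself goes on to distinguish the arms.

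These points narrow the concern without removing it. Discretionary backstops do not mend a written limit that 5 of 5 against 0 of 5 leaves unmet, and none of them schedules a review of complete first-10 data.

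**Conclusion.** The point holds in a limited form. Both first-10 rules pool the arms and so cannot attribute harm to clarithromycin. At 5:5 the hospitalisation rule cannot be met by BiRd events alone; this is arithmetic and needs no assumed rate. Its power of 0.10-0.34 rests on a 5:5 split and assumed rates of 10-20% on Rd and 70-80% on BiRd. The death rule works for BiRd deaths but is weak, at about 0.26-0.28 for a 20% related-death rate with 0-1% on Rd.

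Separately, no scheduled DSMB look is tied to complete 30-day data on the first 10. The figures of day 18-30 and 0-1 closed windows assume even accrual at the planned rates; a slower start would leave more windows closed. This is a weakness in scheduled monitoring that should be corrected. It does not mean that early harm on BiRd would go unseen.

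**What to change.** 1. **Section 9.2.** Resolve the open query over whether the list is included. If the first-10 rules stay, keep the sponsor's thresholds but count by arm, at least for the first 10 treated BiRd subjects.
2. **Section 13.2.** Keep the existing early look. Add a safety review, with counts by arm, once the subjects to whom the rule applies have completed 30 days from the start of therapy: about month 2.3-3.1 for 10 BiRd subjects at planned accrual. Accrual need not pause. A review at 3 months would not reliably serve instead, because at 9 per month the window closes at about day 94 against about day 91.
3. **Section 9.1.** Reconcile the statement that all patients start on BiRd with the randomised arms.

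The cost is a short amendment and one extra DSMB review, with no new data collection. The rule set completes after about 20 patients instead of 10. Applying the rules to both arms raises the chance of a false stop, for example from 0.09 to 0.16 if related deaths are 5% in each arm, or from 0.05 to 0.09 if hospitalisation is 30% in each. Counting only the first 10 BiRd subjects avoids that increase, since at equal rates a set of 10 has the same stopping probability whichever arm it comes from. The amendment should state which option was chosen and why.
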